## 8. PHARMACEUTICAL INFORMATION

A list of the adverse events and potential risks associated with the investigational agents administered in this study can be found in Section 10.1.

### 8.1 CTEP IND Agents

#### 8.1.1 Atezolizumab (NSC 783608)

**Other Names:** TecentriqTM, MPDL3280A

**Classification:** monoclonal antibody

**M.W.:** 150 KD

**Mode of Action:** anti-PD-L1

#### **Description:**

Atezolizumab is a humanized IgG1 monoclonal antibody consisting of two heavy chains (448 amino acids) and two light chains (214 amino acids). Atezolizumab targets human PD-L1 and inhibits its interaction with its receptor PD-1. Atezolizumab also blocks the binding of PD-L1 to B7.1, an interaction that is reported to provide additional inhibitory signals to T cells (Butte *et al.* 2007).

#### **How Supplied:**

Atezolizumab is provided by Genentech/F.Hoffmann-La Roche LTD and distributed by the Pharmaceutical Management Branch, CTEP, NCI. The agent is supplied in a single-use, 20-mL glass vial as a colorless-to-slightly-yellow, sterile, preservative-free clear liquid solution intended for IV administration. Each 20 mL vial contains 1200 mg of atezolizumab and is formulated with glacial acetic acid (16.5 mg), L-histidine (62 mg), polysorbate 20 (8 mg), and sucrose (821.6 mg), with a pH of 5.8. The vial is designed to deliver 20 mL (1200 mg) of atezolizumab solution but may contain more than the stated volume to enable delivery of the entire 20 mL volume.

#### **Preparation:**

The prescribed dose of atezolizumab should be diluted in 0.9% NaCl to a concentration between 3.2 mg/mL and 16.8 mg/mL and infused with or without a low-protein binding 0.2 or 0.22 micrometer in-line filter. The IV bag may be constructed of polyvinyl chloride (PVC), polyolefin (PO), or polyethylene (PE). The prepared solution may be stored at 2°C–8°C for up to 24 hours or at ambient  $\leq$  25°C (77°F) for 6 hours from the time of preparation. If the dose solution is stored at 2°C–8°C (36°F–46°F), it should be removed from refrigeration and allowed to reach room temperature prior to administration. These times include the storage and administration times for the infusion. Do not shake or freeze infusion bags containing the dose solution.

**Storage:** 2°C–8°C (36°F–46°F). Vial contents should not be frozen or shaken and should be protected from direct sunlight.

If a storage temperature excursion is identified, promptly return atezolizumab to 2°C–8°C (36°F–

46°F) and quarantine the supplies. Provide a detailed report of the excursion (including documentation of temperature monitoring and duration of the excursion) to [[contact]](mailto:[contact]) for determination of suitability.

**Stability:** Stability studies are ongoing.

**CAUTION:** No preservative is used in atezolizumab; therefore, the vial is intended for single use only. Discard any unused portion of drug remaining in a vial.

**Route of Administration:** IV infusion

**Method of Administration:**

Atezolizumab is administered as an intravenous infusion over 60 minutes. If the first infusion is tolerated, all subsequent infusions may be delivered over 30 minutes. Do not administer atezolizumab as an intravenous push or bolus. No premedication is indicated for administration of Cycle 1 of atezolizumab. Patients who experience an infusion related reaction with Cycle 1 of atezolizumab may receive premedication with subsequent infusions.

**Potential Drug Interactions:**

Cytochrome P450 enzymes as well as conjugation/glucuronidation reactions are not involved in the metabolism of atezolizumab. No drug interaction studies for atezolizumab have been conducted or are planned. There are no known interactions with other medicinal products or other form of interactions.

**Patient Care Implications:**

Male patients and female patients of childbearing potential should utilize contraception and take active measures to avoid pregnancy while undergoing atezolizumab treatment and for at least 150 days after the last dose of atezolizumab or 3 months after the last dose of cobimetinib.

**Availability**

Atezolizumab is an investigational agent supplied to investigators by the Division of Cancer Treatment and Diagnosis (DCTD), NCI.

8.1.2 [REDACTED]

[REDACTED]

[REDACTED]

[REDACTED]

[REDACTED]

[REDACTED]

The figure consists of a vertical stack of 10 horizontal bars. Each bar is composed of a thick black segment and a thin red segment at its right end. The black segments are of varying lengths, starting with a very short one at the top and increasing in length towards the bottom. The red segments are consistently very short, appearing as small vertical dashes at the end of each bar.

[REDACTED]

[REDACTED]

[REDACTED]

[REDACTED]

[REDACTED]

## Availability

CDX-1127 (varlilumab) is an investigational agent supplied to investigators by the Division of Cancer Treatment and Diagnosis (DCTD), NCI.

### 8.1.3 Cobimetinib (NSC 781257)

**Chemical Name:** (S)-[3,4-difluoro-2-(2-fluoro-4-iodophenylamino)phenyl]  
[3 hydroxy-3-(piperidin-2-yl)azetidin-1-yl]methanone hemifumarate

**Other Names:** COTELLIC®, RO5514041, GDC0973

**Classification:** MEK inhibitor

**Molecular Formula:** C46H46F6I2N6O8  
salt  
531.31 g/mol as free base

**M.W.:** 1178.69 g/mol as hemifumarate

**Approximate Solubility:** At 37°C, the solubility of cobimetinib is 0.744 mg/mL in water

**Mode of Action:** Cobimetinib is a reversible inhibitor of mitogen-activated protein kinase (MAPK)/extracellular signal regulated kinase 1 (MEK1) and MEK2.

**Description:** Cobimetinib API is a hemifumarate salt, appearing as a white to off-white solid.

**How Supplied:** Genentech supplies and CTEP, DCTD, NCI distributes Cobimetinib as a 20-mg film coated, immediate-release tablets debossed on one side with “COB”. Drug concentrations and strengths of tablet drug products are expressed as the free-base equivalents. The tablet formulation consists of the cobimetinib drug product and the following inactive ingredients: microcrystalline cellulose, lactose monohydrate, croscarmellose sodium, magnesium stearate (non-bovine), and Opadry White film coat. All excipients used in the tablet formulation are compendial (USP/NF and/or EP) grade with the exception of the film coating. The tablet coating consists of polyvinyl alcohol-part hydrolyzed, titanium dioxide, macrogol 3350, and talc. The ingredients in the film coating are compendial. Each bottle contains 63 tablets.

**Storage:** Store at room temperature below 30°C (86°F).

If a storage temperature excursion is identified, promptly return cobimetinib to below 30°C and quarantine the supplies. Provide a detailed report of the excursion (including documentation of temperature monitoring and duration of the excursion) to [[contact]](mailto:[contact]) for determination of suitability.

**Stability:** Refer to the package label for expiration.

**Route(s) of Administration:** oral

**Method of Administration:** cobimetinib can be administered with or without food

**Potential Drug Interactions:**

Avoid concurrent use of cobimetinib and strong or moderate CYP3A inhibitors. If concurrent short term (14 days or less) use of moderate CYP3A inhibitors including certain antibiotics (e.g., erythromycin, ciprofloxacin) is unavoidable, consider reducing the dose of cobimetinib while on CYP3A inhibitor. Coadministration of cobimetinib with a strong CYP3A inducer may decrease cobimetinib systemic exposure by more than 80% and reduce its efficacy. Avoid concurrent use of cobimetinib and strong or moderate CYP3A inducers including but not limited to carbamazepine, efavirenz, phenytoin, rifampin, and St. John’s Wort.

Cobimetinib is a substrate of efflux transporter P-glycoprotein (P-gp), but is not a substrate of Breast Cancer Resistance Protein (BCRP), Organic Anion Transporting Polypeptide (OATP1B1 or OATP1B3) or Organic Cation Transporter (OCT1) in vitro. Drugs that inhibit P-gp may increase cobimetinib concentrations. In vitro data suggest that cobimetinib at clinically relevant concentrations does not inhibit P-gp, BCRP, OATP1B1, OATP1B3, OCT1, OAT1, OAT3, or OCT2.

Coadministration of a proton pump inhibitor, rabeprazole 20 mg once daily for 5 days, with a single dose of 20 mg COTELLIC under fed and fasted conditions did not result in a clinically important change in cobimetinib exposure.

**Reproductive Risks:**

Based on its mechanism of action and findings from animal reproduction studies, cobimetinib can cause fetal harm when administered to a pregnant woman. [For this reason, women of child-](#)

bearing potential and men must agree to use adequate contraception (hormonal or barrier method of birth control; abstinence) prior to study entry and, for the duration of study participation, and 5 months after the last dose of Atezolizumab and 3 months after the last dose of cobimetinib.

## Availability

Cobimetinib is an investigational agent supplied to investigators by the Division of Cancer Treatment and Diagnosis (DCTD), NCI.

### 8.1.4 Agent Ordering and Agent Accountability

8.1.4.1 NCI-supplied agents may be requested by eligible participating Investigators (or their authorized designee) at each participating institution. The CTEP-assigned protocol number must be used for ordering all CTEP-supplied investigational agents. The eligible participating investigators at each participating institution must be registered with CTEP, DCTD through an annual submission of FDA Form 1572 (Statement of Investigator), NCI Biosketch, Agent Shipment Form, and Financial Disclosure Form (FDF). If there are several participating investigators at one institution, CTEP-supplied investigational agents for the study should be ordered under the name of one lead participating investigator at that institution.

Sites may order atezolizumab, varlilumab and cobimetinib once a patient has been enrolled to the study .

Submit agent requests through the PMB Online Agent Order Processing (OAOP) application. Access to OAOP requires the establishment of a CTEP Identity and Access Management (IAM) account and the maintenance of an “active” account status, a “current” password, and active person registration status. For questions about drug orders, transfers, returns, or accountability, call or email PMB any time. Refer to the PMB’s website for specific policies and guidelines related to agent management.

8.1.4.2 Agent Inventory Records – The investigator, or a responsible party designated by the investigator, must maintain a careful record of the receipt, dispensing and final disposition of all agents received from the PMB using the appropriate NCI Investigational Agent (Drug) Accountability Record (DARF) available on the CTEP forms page. Store and maintain separate NCI Investigational Agent Accountability Records for each agent, strength, formulation and ordering investigator on this protocol.

### 8.1.5 Investigator Brochure Availability

The current versions of the IBs for the agents will be accessible to site investigators and research staff through the PMB OAOP application. Access to OAOP requires the establishment of a CTEP IAM account and the maintenance of an “active” account status, a “current” password and active person registration status. Questions about IB access may be directed to the PMB IB Coordinator via email.

## 9. STATISTICAL CONSIDERATIONS

### 9.1 Study Design/Endpoints

The proposed study is an open-label, randomized phase 2 trial evaluating atezolizumab in combination with CDX-1127 (varlilumab) with or without the addition of cobimetinib in unresectable, pre-treated cholangiocarcinoma. Patients will be randomized in a 1:1 ratio to the two arms. The primary objective of the trial is to determine whether the combination of checkpoint blockade with an immune co-stimulatory yields a clinically compelling antitumor activity (measured as overall response rates [ORR, assessed by RECIST 1.1] and progression free survival [PFS, assessed by RECIST 1.1]) and if this effect can be further amplified with the addition of MEK inhibition. Secondary endpoints include safety, overall survival (OS), immunologic correlates, and pharmacokinetics of atezolizumab and varlilumab. Objective response (OR) and PFS are co-primary endpoints.

#### Analysis of Co-Primary Efficacy Endpoints

##### Overall Response Rate (ORR):

The objective response rate defined as the proportion of response evaluable subjects who have a complete response (CR) or partial response (PR) using RECIST 1.1 criteria at any time during the study. The evaluable population includes all subjects who initiated therapy. Patients who have not received a follow-up scan, and thus are not evaluable for response, will be counted as non-responders.

##### Progression Free Survival (PFS):

PFS is defined as the duration of time from date of randomization to time of progression or death. This analysis is intent-to-treat including all randomized patients. Patients who come off of study treatment for clinical progression without radiographic progression (i.e. clinical progression) will be coded as progression for the analysis, and the date of progression is the date of clinical progression. Due to the rapid progression of the disease in the majority of patients, little loss to follow up is expected, but subjects who are lost to follow-up as of the data analysis cutoff date will be right-censored. The censoring date will be determined from the date the subject was last evaluated for progression. PFS within each treatment arm will be summarized descriptively using Kaplan-Meier plots, and compared between arms using log-rank tests.

### 9.2 Sample Size/Accrual Rate

The study is planned for 64 evaluable subjects (32 subjects per treatment arm). The objective response rate (ORR) of BTCs treated with FOLFOX, anti-PD-1 monotherapy or anti-PDL1+MEKi is around 5%. A clinically meaningful improvement that warrants further study would be a 20% ORR. A Simon two-stage minimax design is planned for each arm. Arm specific type I error is set at 0.1 (one-sided) when evaluating the co-primary endpoints of ORR and PFS. For each arm, 18 patients will be enrolled in the first stage. If none have OR, the accrual to that arm will be terminated. If 1 or more respond, then additional 14 patients will be enrolled (for a total of 32 patients in that arm). If 4 or more patients achieve OR (12.5%) in stage 1 and stage 2 combined, the endpoint is met in that arm. The design yields at least 90% power to detect a true

response rate of at least 20%, with at least .90 probability of a negative result (no more than 3 responses if the true response rate is no more than 5%, for each of the two arms. The chance of early stopping after stage 1 in each arm is 0.4 when the true response rate is 5%.

If both arms meet the response endpoint criteria, the comparison of PFS will be performed. The median progression free survival of BTCs treated with FOLFOX, anti-PD-1 monotherapy, & anti-PDL1+MEKi is 4.0, 2.0, and 3.5 months, respectively. Randomization of 64 patients, with observation of 55 PFS events would yield 90% power to detect an HR = 0.5 (corresponding to 3.5 vs. 7 months median PFS in the doublet and triplet arm, respectively), at the one-sided 0.10 significance level. An observed 40% increase in median PFS for the triplet arm (approximately 1.4 months, assuming an approximately 3.5-month median PFS in the doublet arm; observed HR=0.714) would be sufficient to achieve statistical significance.

Taking into account dropout/study attrition, we anticipate screening between 70-80 patients in order to achieve 32 evaluable patients per treatment arm (N=64) with an anticipated accrual rate of 4 patients/month.

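### Section 9.2 runs the between-arm PFS test only if both arms meet the ORR rule, 9.1 and 12.1.6 set no such condition, and the 90% power and the HR 0.714 threshold need correcting to match

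*Combined protocol and SAP*

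**What the plan says.** Section 9.1 states that "Objective response (OR) and PFS are co-primary endpoints". Its primary objective is whether the doublet has compelling activity and "if this effect can be further amplified with the addition of MEK inhibition". "Patients will be randomized in a 1:1 ratio to the two arms".

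Section 9.2 judges ORR arm by arm with a two-stage rule. Each arm enters 18 patients and stops if none responds; otherwise it continues to 32 and succeeds with 4 or more responses. The design is described as having at least 90% power for a true "response rate of at least 20%, with at least .90 probability of a negative result" when the true rate is 5% or less.

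For PFS, 9.2 first sets a condition: "If both arms meet the response endpoint criteria, the comparison of PFS will be performed". Later in the same paragraph it says that 64 randomized patients "with observation of 55 PFS events would yield 90% power to detect an HR = 0.5", at one-sided 0.10, corresponding to medians of 3.5 and 7 months. It adds that a 40% observed increase in median PFS ("observed HR=0.714) would be sufficient to achieve statistical significance").

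The PFS definition under 9.1 covers all randomized patients and says: "PFS within each treatment arm will be summarized descriptively using Kaplan-Meier plots, and compared between arms using log-rank tests". Section 12.1.6 repeats that sentence. Neither place mentions a response condition.

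**The concern.** ORR is compared with a fixed 5% in each arm separately. The log-rank test is therefore the only stated between-arm test of a primary endpoint, and it carries the question of what cobimetinib adds.

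The plan gives two different rules for when that test is run. Suppose one arm ends with 3 of 32 responses. Under 9.2 there is no comparison; under 9.1 and 12.1.6 there is one. If the choice is not fixed in advance, the status of a co-primary test in an open-label trial can be settled after the response counts are known.

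The power statement has the same root. If the gate governs, the chance of a positive PFS result includes the chance of reaching the test, and the quoted 90% leaves that step out without saying so. The stated significance threshold is a smaller, separate matter: a result at exactly that value would contradict the protocol's own sentence.

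**Working it through.** **Inputs, all from 9.1 and 9.2:** 1:1 allocation; 18 then 14 patients per arm; stop at 0/18; success at 4 or more of 32; ORR 5% (null) and 20% (target); 55 PFS events; HR 0.5; one-sided alpha 0.10 (z = 1.2816). The 30% ORR values below are assumptions of this review. They lie within the plan's alternative of 20% or more.

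**The plan's own figures**

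- PFS power = Φ(ln 2 × √55 / 2 − 1.2816) = Φ(2.570 − 1.282) = 0.901. The stated 90% reproduces.
- ORR, per arm, with X1 ~ Bin(18, p) and X2 ~ Bin(14, p): P(pass) = P(X1 + X2 ≥ 4) − P(X1 = 0) × P(X2 ≥ 4).
  - At 5%: pass 0.072, early stop 0.95^18 = 0.397. The stated limits (at most 0.10, and 0.4) reproduce.
  - At 20%: pass 0.9015, early stop 0.8^18 = 0.018, complete accrual but miss 0.0805. The stated power of at least 90% reproduces.
  - At 30%: pass 0.9935, early stop 0.0016, complete but miss 0.0049.

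**If the gate in 9.2 governs**

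The arms are independent, so P(gate open) is the product of the two pass probabilities. Taking response and PFS as independent, overall PFS power = P(gate open) × 0.901. The contested situation, in which both arms complete accrual and at least one misses 4/32, has probability P(both clear stage 1) − P(gate open).

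| True ORR, two arms | Gate open | Overall PFS power | Both complete, at least one misses | At least one arm stops at stage 1 |
|---|---|---|---|---|
| 20% / 20% | 0.9015² = 0.813 | 0.732 | 0.964 − 0.813 = 0.152 | 0.036 |
| 20% / 30% | 0.9015 × 0.9935 = 0.896 | 0.807 | 0.980 − 0.896 = 0.085 | 0.020 |
| 30% / 30% | 0.9935² = 0.987 | 0.890 | 0.997 − 0.987 = 0.010 | 0.003 |

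**Does independence of response and PFS matter?** It was checked by simulation (6,000 trials per case, exponential PFS with medians 3.5 and 7 months, log-rank at 55 events), linking response to PFS with a latent correlation from 0 to 0.9. The probability of an open gate and a significant test was 0.73 to 0.75 at 20%/20%, 0.79 to 0.81 at 20%/30% and 0.88 to 0.89 at 30%/30%. The product is a fair approximation.

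**If 9.1 and 12.1.6 govern as written**, the test is run whatever the response counts, and power stays at about 90% whenever both arms complete accrual.

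**Threshold for significance at 55 events**

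- Critical HR = exp(−2 × 1.2816 / √55) = exp(−0.3456) = 0.708.
- As an increase in the median: 1/0.708 = 1.413, or +41.3%, which on 3.5 months is 1.44 months.
- At HR 0.714: z = −ln(0.714) × √55 / 2 = 1.249, one-sided p = 0.106, above 0.10.

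**The case against.** The best reply is that nothing in the power calculation is wrong. The 90% reproduces, the gate sentence opens the same paragraph, and the power of a later, gated test is naturally quoted for that test. The plan never claims 90% as the overall chance of success. This stands as far as it goes: 90% is a correct conditional figure. It does not remove the need to label it, because two other sections describe the same test without the gate and a reader cannot tell whether the condition applies.

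It is also fair that the overall figure depends on the scenario. It runs from 73% to 89% over the cases shown, and the plan itself gives only 5% and 20% as response rates. The 20%/20% case uses the plan's own target; the others should be labelled as assumptions.

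The HR 0.714 sentence is an illustration. The decision will rest on the log-rank p-value, so no sample size, event count or rule changes. It is still incorrect as written.

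Two stronger readings should be resisted. A reader might infer that the plan is silent on PFS when an arm misses 4/32. It is not: 9.1 and 12.1.6, read literally, prescribe Kaplan-Meier summaries and a log-rank comparison of all randomized patients in that case too. The fault is a conflict with 9.2. A reader might also infer that the true PFS power is simply 73%. That holds only if 9.2 overrides the other two sections, and only at 20% ORR in both arms.

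**Conclusion.** The point holds as a conflict that must be resolved before data are seen. Section 9.2 gates the PFS comparison on both arms meeting the ORR rule, 9.1 and 12.1.6 do not, and no section says which governs. The sections collide whenever both arms complete accrual and at least one misses 4/32: probability 0.15 at 20%/20% ORR, falling to 0.085 and 0.010 in the two more favourable cases.

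If the gate governs, the 90% is conditional, and overall PFS power for HR 0.5 is about 73% at the plan's target ORR in both arms, about 81% at 20%/30% and about 89% at 30%/30%. These figures rest on 55 events, one-sided 0.10 and approximate independence of response and PFS; the simulations show that the last assumption matters little.

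The statement that an observed HR of 0.714 reaches significance is wrong at 55 events by a small margin (p = 0.106; boundary about 0.708). The review takes no view on whether gating is the better design; either choice is open to the sponsor.

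**What to change.** 1. In 9.1, 9.2 and 12.1.6, state before data are seen whether the ORR gate governs the between-arm log-rank test. If it does, say that PFS is reported descriptively when either arm misses the ORR rule. If it does not, remove the condition from 9.2.
2. If the gate governs, describe the 90% in 9.2 as conditional on both arms meeting the ORR rule. Add the overall power: about 73% when the true ORR is 20% in both arms, with the values for higher ORR (about 81% at 20%/30%, 89% at 30%/30%) marked as assumptions.
3. In 9.2, replace the 40% increase and HR 0.714 by an increase of about 41% and HR 0.708 at 55 events. The approximate 1.4 months can stay.

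This is wording in three sections. It needs no extra patients, visits or data and no change of design. The downside is that the stated power looks less favourable.
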